## Protocol Title

### **A Randomized Study of an Alternate Dosing Protocol for Magnesium Sulfate in Obese Preeclamptic Women**

**Objectives.** In the current proposed study, we hope to identify pharmacokinetic (PK) drug effects (a therapeutic serum magnesium level) that an alternate magnesium sulfate dosing regimen will achieve in obese preeclamptic pregnant women.

#### **Specific Aim 1: To determine if an alternate magnesium sulfate dosing regimen in preeclamptic pregnant women with $\text{BMI} \geq 35 \text{ kg/m}^2$ will result in a larger proportion of obese women who have therapeutic serum magnesium levels ( $\geq 4.8 \text{ mg/dL}$ ) for seizure prophylaxis after 4 hours of administration.**

Aim 1a: To determine if an alternate magnesium sulfate dosing regimen in preeclamptic pregnant women with  $\text{BMI} \geq 35 \text{ kg/m}^2$  will result in a larger proportion of obese women who have therapeutic serum magnesium levels ( $\geq 4.8 \text{ mg/dL}$ ) for seizure prophylaxis at the time of delivery compared to a current standard dosing protocol.

#### **Specific Aim 2: To determine if, and which, maternal side effects are more common at 1 hour, 4 hours, and time of delivery with an alternate magnesium sulfate dosing protocol in obese women.**

## Hypotheses

We hypothesize that a randomized trial of alternate dosing of intravenous magnesium in obese women will allow us to:

1. Determine optimal antenatal magnesium dosing protocols to optimize therapeutic serum magnesium levels in obese preeclamptic women.
2. Determine significant covariates and correlations between maternal serum magnesium levels and maternal side effects and outcomes.
3. Determine the optimal antenatal magnesium dose to minimize adverse drug effects while maintaining a therapeutic serum magnesium level in the mother.

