## Background

Magnesium sulfate is one of the most commonly prescribed intravenous medications in contemporary obstetric practice. Magnesium is the drug of choice for preventing seizures in women with preeclampsia, a leading cause of maternal morbidity and mortality. More than 77% of expectant mothers experience side effects related to antenatal magnesium administration. Magnesium may also negatively impact obstetric outcomes and lead to adverse neonatal effects. Current intravenous magnesium treatment for various indications (preeclampsia, tocolysis, neuroprotection) follows standardized protocols (4-6 g loading dose followed by an infusion at 1-2 g/h) based on institution preference. These protocols proposed by Prichard in 1979 were derived clinically to provide estimated serum magnesium levels necessary to treat eclamptic seizures. These standardized protocols are administered unaltered to all patients, without adjustment for maternal or fetal factors that may affect serum magnesium levels. The PI has previously constructed a detailed, robust pharmacokinetic (PK) model of intravenous magnesium sulfate administered antenatally to expectant mothers and exposed fetuses with the aim of optimizing maternal and fetal outcomes while preventing maternal and neonatal overdosing and morbidity associated with current magnesium treatment protocols.

The PK data derived from this pilot study at another academic institution suggests obese pregnant women may require an increased dose of magnesium sulfate to maintain a therapeutic serum level for prevention of eclamptic seizures ( $\geq 4.8$  mg/dL). In that pilot study, statistical modeling suggested more obese preeclamptic women take approximately twice as long as non-obese preeclamptic women to achieve steady state levels of the drug.

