## **Number of Subjects**

Based on a previous retrospective study conducted by Tudela et al and our own pilot data, we estimate that 50% of obese women will be subtherapeutic for eclamptic seizure prophylaxis 4 hours after magnesium sulfate administration. Assuming 95% of normal weight women have therapeutic serum magnesium levels after 4 hours of administration, we anticipate that 18 patients (36 total) are needed in each dosing group to detect a 50% difference in the proportion of women with a  $\text{BMI} \geq 35 \text{ kg/m}^2$  who have therapeutic magnesium levels 4 hours after magnesium sulfate administration. Based on current patient load, which includes treatment of approximately 40 preeclamptic patients per month, and the additional inclusion criteria of the disease severity requiring magnesium sulfate administration, as well as a maternal  $\text{BMI} \geq 35 \text{ kg/m}^2$ , and anticipated number of patients declining study participation, we anticipate potential enrollment of 1-2 women and their neonates per week.

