## **2. Procedures Involved**

After obtaining informed consent, the subject will be randomly assigned to one of two treatment groups: 1.) a starting dose of magnesium sulfate of 4g, followed by 1g every hour until 24 hours after delivery (the current standard regimen used at OHSU), or 2.) a starting dose of magnesium sulfate of 6g, followed by 2g every hour until 24 hours after delivery. There will not be a placebo arm of the study; only a smaller dose or larger dose of magnesium sulfate administered. Although the study dosing is randomized, it is not blinded and both the investigator and the research subject may know what dose of magnesium sulfate is being administered. If the subject is found to be symptomatic at any point in the study, the usual clinical care will be provided, which would include checking a serum magnesium level and decreasing the dose of magnesium sulfate, if needed. Study participation will continue; however, the timing and details of the dosing change will be recorded and used for research purposes.

If there is an indwelling intravenous catheter in place for surgery, we will attempt to use it to draw blood. We will draw a sample from a vein if we are not able to collect the samples from an existing intravenous catheter.

Specimens will be collected as follows:

- Serum magnesium before the administration of magnesium sulfate
- Serum magnesium at 1 hour, 4 hours, and delivery after the initial dose of magnesium sulfate
- Each sample will be 5-10 ml (approximately 1-2 teaspoon). The total drawn for all samples will likely not exceed 5 teaspoons.
- Urine samples will be obtained if possible at these same time points.
- If the patient requires spinal anesthesia for cesarean delivery, 0.5 ml (a few drops) of spinal fluid will be taken to check for magnesium levels at the same time the spinal anesthetic is being performed.

	Visit 1 Day 1	Visit 2 Day 1	Visit 3 Day 1	Visit 4 Day 1
Consent Discussion, Screening tests and medical history	X			
Blood draw (1 teaspoon)	X	X	X	X
Urine sample (2 teaspoons)	X	X	X	X
Time (after magnesium sulfate administration)	baseline	1 hour	4 hours	Time of delivery (within 20 mins)

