**Information that may be abstracted from the subject's chart includes** maternal age, race, height, weight, renal function and creatinine clearance (if available), maternal heart rate variability, medical comorbidities, chorioamnionitis, labor duration, mode of delivery, gestational age, cord pH, and birthweight. These covariates may be considered in the pharmacokinetic model. These covariates demonstrate biological plausibility, and have physiologic potential to significantly impact the optimal dosing of magnesium. Additionally, maternal side effects (flushing, sedation, nausea, vomiting, respiratory rate, oxygen saturations, blood pressure, heart rate, and patella tendon reflex depression) will be assessed prospectively by a physician or research assistant at the same time-points as the PK sampling. Neonatal data will include NICU admission, need for respiratory support, need for blood pressure support, electrolyte abnormalities, feeding difficulties, intraventricular hemorrhage, necrotizing enterocolitis, seizures, sepsis, respiratory distress syndrome, retinopathy, patent ductus arteriosus, fetal/infant death.

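### Aim 2 compares only how common side effects are, with no severity grade specified; at 18 women per arm a present/absent comparison can show only very large differences and cannot show a rise in severity alone.

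*Combined protocol and SAP*

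**What the plan says.** Specific Aim 2 is framed on frequency: "To determine if, and which, maternal side effects are more common at 1 hour, 4 hours, and time of delivery". It has two parts: whether side effects are more common at all, and which ones, at three time points.

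The Background gives one rate: "More than 77% of expectant mothers experience side effects related to antenatal magnesium administration". No dose, symptom or time point comes with it.

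Section 2 (Procedures Involved) lists the items as "maternal side effects (flushing, sedation, nausea, vomiting, respiratory rate, oxygen saturations, blood pressure, heart rate, and patella tendon reflex depression". They "will be assessed prospectively by a physician or research assistant at the same time-points as the PK sampling", so a physician or research assistant is already due to check the woman each time. Four of the nine items are vital signs with numeric values. The other five have no grade or scale. For women who become symptomatic and have their dose altered, "the timing and details of the dosing change will be recorded and used for research purposes". The same section says that the dosing is not blinded.

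Section 4 (Data Analysis) models serum magnesium only. The sample size ("18 patients (36 total) are needed in each dosing group to detect a 50% difference") is set for the 4-hour magnesium level. No power is stated for Aim 2.

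**The concern.** Hypothesis 3 seeks a dose that limits adverse effects while keeping the serum level therapeutic, and Aim 2 is the only aim that addresses side effects. A frequency comparison scores mild flushing and severe flushing alike. If most women on either regimen have some side effect, a pooled yes/no comparison also leaves limited space for the alternate arm to be worse. The alternate arm has twice the hourly infusion of the standard arm, so a finding of no difference could be read as reassurance that the measure was unable to give. Severity that is not recorded at the bedside cannot reliably be recovered later.

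**Working it through.** **Inputs.** 18 per arm, 36 in total, 1:1 (Number of Subjects; Study Design). Any-side-effect rate 77%, taken from the Background and *assumed* here to be the standard-arm rate. The documents state no alpha, sidedness or power, so I assume 5% two-sided and no missing data.

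**The plan's own figure.** The inputs are "we estimate that 50% of obese women will be subtherapeutic for eclamptic seizure prophylaxis 4 hours after magnesium sulfate administration" and "Assuming 95% of normal weight women have therapeutic serum magnesium levels after 4 hours of administration". The formula is

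n per arm = [z(1−α/2)·√(2p̄(1−p̄)) + z(1−β)·√(p₁(1−p₁) + p₂(1−p₂))]² / (p₂−p₁)².

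For 50% v 95%, p̄ = 0.725.
- 80% power: (1.96×0.631 + 0.842×0.545)²/0.2025 = 14.2, so 15, or 19 with continuity correction.
- 90% power: 18.5, so 19 without correction.

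The stated 18 is therefore consistent with Aim 1 under common choices. Exact Fisher power at 18 per arm is 84%.

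**Any side effect, from 77%.** Fisher power by summing the binomial probabilities of all outcomes with p ≤ 0.05; n from the formula above.

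| Alternate arm | Fisher power, 18 per arm | Normal approximation | n per arm for 80% (with continuity correction) |
|---|---|---|---|
| 85% | 4% | 9% | 377 (401) |
| 90% | 9% | 18% | 127 (142) |
| 95% | 20% | 34% | 58 (68) |
| 100% | 40% | 59% | 29 (38) |

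If all 18 women in the alternate arm are affected, 14/18 in the standard arm gives p = 0.10 and 13/18 gives p = 0.045. From a 77% base, then, no possible rise reaches 80% power.

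**If the standard-arm rate is lower.** Fisher power against 95% is 38% from 70%, 65% from 60% and 84% from 50%.

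**Single symptoms.** The documents give no per-symptom rates. For illustration, if 77% were the union of k equally common, independent symptoms, each would have rate 1 − 0.23^(1/k): 39% for k = 3 and 22% for k = 6. A 23-point rise from anywhere in 22–39% has Fisher power of about 21%. To reach 80% power, the rate must rise from 10% to 58%, from 30% to 80%, or from 50% to 94% (Fisher, 2-point grid).

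**What grading would add.** The severity splits are assumed, with four grades, and a Wilcoxon rank test is simulated.
- Odds shift of 4 from 77% affected: odds 0.77/0.23 = 3.35, times 4 = 13.4, so 93% affected. Rank test about 58–63%, present/absent 14–17%, over several splits.
- Odds shift of 4 from 30% affected: odds 0.43, times 4 = 1.71, so 63% affected. Rank test about 55%, present/absent about 44%.
- Severity only, with 77% affected in both arms (none/mild/moderate/severe 23/50/20/7% v 23/17/30/30%): rank test about 33%, present/absent about 2%, which is just the Fisher test's false-positive rate.

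That 2% also shows Fisher to be conservative here, so part of each gap comes from the choice of test and not from the grades.

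**The case against.** A reader might infer that the 77% figure puts the whole of Aim 2 at a ceiling, with almost no room to rise, so that the trial is bound to miss a large worsening. The documents do not support that, for five reasons.

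- The 77% is a per-woman, any-effect rate. It does not carry over to flushing at 4 hours or vomiting at delivery, and Aim 2 also asks which effects differ.
- It is not shown to be the standard-arm rate. The reference cited for it is a trial of cerebral palsy prevention. Study Design says that women under 32 weeks at this hospital receive the alternate-arm regimen for fetal neuroprotection. The standard-arm rate could be lower.
- Twenty-three points is real room. At 18 per arm a 23-point rise is easier to detect from 77% (40%) than from 30% (21%). The small sample causes much of the low power.
- Present/absent recording is inferred from the wording of Aim 2 and the lack of any grade. The data form is not in the documents, and four items are numeric.
- Recorded dose changes are an indirect sign of severity.

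All five stand as limits on the claim. They do not supply a grade, an analysis of the vital signs or dose changes, or power for a yes/no comparison.

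**Conclusion.** The point holds as a gap in measurement and analysis. As written, Aim 2 invites a frequency comparison that at 18 per arm detects only very large differences: none achievable with 80% power for any side effect from a 77% base, and rises of about 44–50 points for single symptoms with base rates of 10–50%. A change in severity alone would be invisible to it.

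The Fisher figures rest on the assumed alpha and on 77% applying to the standard arm; a base near 50–60% would be materially better. The ordinal figures rest on invented severity splits. They show that grading gains power, by roughly 11 points (55% v 44%) to over 40 (58% v 14–17%) at an odds shift of 4, but they do not promise 80%. This should be changed because it is cheap and the information is lost otherwise. It does not affect Aim 1.

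**What to change.** 1. On the side-effect form, at each scheduled check, record flushing, sedation, nausea and vomiting as none, mild, moderate or severe, and reflexes on a graded scale. If the form already does this, say so in Section 2.
2. In Section 4, for each of these five items at 1 hour, 4 hours and delivery, add an ordinal between-arm comparison (rank test or proportional-odds model) beside the present/absent rates. This keeps the *which* and *when* of Aim 2. Use the worst grade per woman as one overall summary for the *if* question, and not as a replacement. Five items at three times make 15 comparisons, so report estimates with intervals.
3. Analyse respiratory rate, oxygen saturation, blood pressure and heart rate as continuous values.
4. State that a finding of no difference at this sample size does not show similar tolerability.

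**Cost.** One extra column on the form and a rewording of Aim 2 and Section 4; no added visits, samples or staff. The main downside is that grades are subjective and the trial is unblinded, so both assessor and patient can bias them. The report should say so.

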**4. Data Analysis**

Univariate and multivariate mixed-effects modeling will be utilized to assess the impact of various covariates on the outcome of serum magnesium level at different time points after magnesium sulfate administration. As previously described, assuming 95% of normal weight women have therapeutic serum magnesium levels after 4 hours of administration, we anticipate that 18 patients (36 total) are needed in each dosing group to detect a 50% difference in the proportion of women with a  $\text{BMI} \geq 35 \text{ kg/m}^2$  who have therapeutic magnesium levels 4 hours after magnesium sulfate administration. Based on current patient load, which includes treatment of approximately 40 preeclamptic patients per month, and the additional inclusion criteria of the disease severity requiring magnesium sulfate administration, as well as a maternal  $\text{BMI} \geq 35 \text{ kg/m}^2$ , and anticipated number of patients declining study participation, we anticipate potential enrollment of 1-2 patients per week.

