## **7. Risks and Benefits**

### **a. Risks to Subjects.**

The possible risks of obtaining blood samples from a vein in the arm are pain, bruising, fainting, and rarely, infection. This risk is extremely small as sterile supplies will be used, and all hospital protocols will be followed.

Magnesium sulfate is known to have associated side effects (i.e. nausea, flushing, palpitations, headache, malaise, sweating, pulmonary edema, and loss of reflexes.) There may be some side effects we do not expect because we are still learning about different dosing of the study drug. The study drug may be discontinued or the dosing changed if subjects experience serious side effects.

One risk to taking part in this study is that the study drug or the dose administered may not be effective in helping to treat preeclampsia. This is a risk for all patients who are administered magnesium sulfate.

There are several drugs (prescription and non-prescription) that may cause problems when taken with the study drug. The investigator will carefully review all of the drugs a potential subject is taking before administering the study drug.

Possible risks of the study include a low risk of breach of confidentiality.

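### The Aim 2 side-effect checklist omits five effects the protocol itself names as known, and with no stated analysis it invites up to 27 unadjusted comparisons at 18 women per arm

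*Combined protocol and SAP*

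**What the plan says.** Specific Aim 2 sets the question: "To determine if, and which, maternal side effects are more common at 1 hour, 4 hours, and time of delivery" with the alternate regimen in obese women. Section 2 (Procedures Involved) lists what is assessed: "flushing, sedation, nausea, vomiting, respiratory rate, oxygen saturations, blood pressure, heart rate, and patella tendon reflex depression". These "will be assessed prospectively by a physician or research assistant at the same time-points as the PK sampling", which means baseline, 1 hour, 4 hours and delivery.

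Section 7a (Risks to Subjects) gives the known effects of the drug as "nausea, flushing, palpitations, headache, malaise, sweating, pulmonary edema, and loss of reflexes".

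Section 4 (Data Analysis) is the only analysis section. It describes mixed-effects models for the effect of covariates "on the outcome of serum magnesium level at different time points" and repeats the sample size. It gives no method, summary measure, vital-sign threshold, alpha or exploratory label for side effects, and neither does any other section. Sample size is set on the 4-hour magnesium level alone: "we anticipate that 18 patients (36 total) are needed in each dosing group to detect a 50% difference" (Number of Subjects). Section 2 also says that treatment is not blinded.

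**The concern.** The third hypothesis says the trial will find the dose that keeps adverse effects low while holding a therapeutic level. Side effects are therefore half of the stated trade-off, even though the trial is not sized on them. Two features weaken that half.

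- **Ascertainment.** An effect that is not on the checklist is recorded only if someone raises it. In an open-label trial, the readiness to raise it can differ by arm, so a comparison on those effects could be biased in either direction.
- **Analysis.** An aim that asks which effects differ, with no analysis stated, leaves the analyst free to compare each item at each time. A chance difference could be reported as a side effect of the higher-dose arm, or a non-significant one could be taken to show that the regimens are equally well tolerated.

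**Working it through.** **1. The two lists.** Section 7a names eight effects. Nausea and flushing are on the section 2 checklist, and loss of reflexes matches its patellar reflex item. That leaves 8 - 3 = 5: palpitations, headache, malaise, sweating and pulmonary edema. None of the five is in the chart-abstraction list either. Section 6 provides for review of adverse events when investigators or staff report them, which is not a scheduled question put to both arms.

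**2. The plan's own figure.** The 18 per arm concerns therapeutic magnesium at 4 hours. The inputs are 50% v 95% (Number of Subjects), or 45% v 95% if the stated 50-point difference is taken literally. Alpha and power are not stated, so I assume two-sided 0.05. The formula is n = [1.96√(2p̄q̄) + z_β√(p₁q₁ + p₂q₂)]²/d², with continuity correction n' = (n/4)[1 + √(1 + 4/(nd))]².
- 50% v 95%, 80% power: n = 14.2, corrected 18.4, so 19.
- 45% v 95%, 85% power: n = 13.4, corrected 17.2, so 18.

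The figure is reproduced to within a patient or so. It says nothing about Aim 2.

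**3. How many comparisons are possible.** 9 items × 3 post-dose times = 27.

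**4. Chance of at least one p ≤ 0.05 with no true effect on any item.**
- Independent two-sided tests of true size 5%: 1 - 0.95^27 = 75%. At pairwise correlation 0.2 it is 69%, and at 0.5 about 49% (simulation).
- Fisher's exact test at 18 v 18 has true size 0.9% at a 10% event rate and 2.9% at 50%. Over 27 independent tests, that gives 22% to 55%.
- Simulation with five binary items and four continuous vital signs, from zero to strong within-woman correlation: 59% down to 36% with Fisher plus t-tests, and 74% down to 49% with chi-square plus t-tests.
- Simulation with all nine items binary at mixed rates of 5% to 50%: 38% down to 28% (Fisher), and 70% down to 53% (chi-square).
- Counting only false signals towards more side effects with the alternate regimen: 1 - 0.975^27 = 50% if independent. In the all-binary simulation it is 21% down to 14% (Fisher) and 44% down to 28% (chi-square).

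Item rates are assumed. The documents give only one rate, more than 77% with any side effect (Background), and it is not split by item, time or arm. If every item had a rate of 5%, 27 independent Fisher tests would give only 3%.

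**5. What a non-significant result can exclude.** The 95% half-width for a difference is 1.96√(2p(1 - p)/18), with p the rate in each arm.

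| Event rate in both arms | Half-width (points) |
|---|---|
| 10% | 20 |
| 20% | 26 |
| 30% | 30 |
| 50% | 33 |

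For true differences of 20 points (10% v 30%, 20% v 40%, 30% v 50%), Fisher power is 20%, 16% and 16%. The uncorrected formula in step 2 needs 62, 82 and 93 per arm for 80% power. At base rates of 10% to 50%, 80% power (normal approximation) needs a difference of about 42 to 46 points. With 0 of 18 events, the exact upper 95% limit is 1 - 0.025^(1/18) = 18.5%.

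**6. Effect of the fix on the count.** Adding five items makes 14. Tested item by time, that would be 14 × 3 = 42 comparisons. With one estimate per item it is 14. The expected number of 95% intervals that exclude zero by chance is then 14 × 0.05 = 0.7, against 27 × 0.05 = 1.35 for the present list taken item by time.

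**The case against.** The strongest reply is that the protocol plans no side-effect tests at all, so the 27 comparisons are the reader's construction. That stands: the documented facts are an aim that asks which effects differ and no analysis to answer it. A reader might infer that the plan commits to 27 tests and disregards the baseline assessment. The documents say neither.

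A reader might also infer that a false signal is more probable than not. The 75% needs independent two-sided tests of true size 5% and no real dose effect. Correlation, exact tests and counting one direction all lower it, some below one in four. Substantial is as far as the figures go.

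Nor is a null result empty. It could argue against differences of about 45 points or more. What it cannot do is exclude moderate ones.

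On the omitted effects, section 7a is a risk disclosure and not an endpoint list. Section 6 covers adverse events in general, and section 2 provides for care of symptomatic women. So it goes too far to say that nothing could be learned about the five. What is missing is systematic, by-arm ascertainment, and that gap remains.

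The second hypothesis mentions correlating serum level with side effects, but that is not a comparison of randomised arms. Finally, formal multiplicity adjustment of tolerability outcomes would cut the already low power to detect harm. An any-symptom composite would sit near a ceiling, given the rate above 77%. I ask for neither.

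**Conclusion.** The point holds as a cheap improvement. The omission of five named effects from the checklist is plain from setting sections 2 and 7a side by side, and rests on no calculation. The analysis gap matters because of its consequences if the items are compared one by one. The chance of at least one false signal is roughly one in three to three in four two-sided, and about half that towards more side effects. Non-significant differences would leave about 20 points open in either direction at a 10% event rate, and more at higher rates. These figures assume 18 analysed per arm, two-sided 0.05, no true effect for the false-signal figures, and item rates mostly between 10% and 50%. The false-signal chance is lower if most items are rare. The documents do not support the stronger claims that the trial has committed to 27 tests or that Aim 2 can yield nothing.

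**What to change.** Before any data are seen by arm:

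1. Add palpitations, headache, malaise, sweating and pulmonary edema to the existing checklist, assessed in both arms at baseline, 1 hour, 4 hours and delivery.
2. Give one baseline-referenced estimate per item across the three post-dose times, by randomised arm. For vital signs, use a baseline-adjusted repeated-measures model. For symptoms and signs, use the risk difference, with 95% CI, for a new or worsened finding at any of the three times, with a simple or exact method where events are rare.
3. Label Aim 2 exploratory, and state that a non-significant difference will not be read as equal tolerability.

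The cost is five more checklist items at visits already planned, some analysis-plan wording, and fewer item-level significance claims. No extra women, visits or samples are needed. The change does not raise power, so moderate differences will stay unresolved at 18 per arm. That is why the third step is needed.

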## **6. Provisions to Monitor the Data to Ensure the Safety of Subjects**

The investigators and study staff are responsible for recording the data, and they will be verifying its accuracy throughout the process. The PI will be reviewing the data in-depth periodically throughout the study. The PI will also be overseeing that the study procedures are being carried out as per the approved protocol via close supervision of the study visit and procedures and through frequent communication with the other investigators and staff. Anytime that an AE, SAE, UP or protocol deviation is reported by an investigator or study staff, the PI will review and assess the data, and proceed as per OHSU reporting policy. Otherwise, the PI entity will be reviewing the records periodically throughout the study. All adverse events will be assessed and reportable UPs will be submitted to the IRB, if judged related to the study protocol. All data will be stored for future analysis and stored in the MFM Repository eIRB#7285

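### Aim 2 counts side effects only at scheduled checks, and no stated comparison of arms uses the symptom-driven dose changes or adverse events recorded between them

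*Combined protocol and SAP*

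**What the plan says.** Specific Aim 2 is a comparison at set times: whether, and which, "maternal side effects are more common at 1 hour, 4 hours, and time of delivery with an alternate magnesium sulfate dosing protocol". The paragraph on chart abstraction in section 2 (Procedures Involved) matches it. The listed side effects "will be assessed prospectively by a physician or research assistant at the same time-points as the PK sampling", and the visit table puts those at baseline, 1 hour, 4 hours and delivery.

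Section 2 also expects symptoms at other times. "If the subject is found to be symptomatic at any point in the study", then "the usual clinical care will be provided, which would include checking a serum magnesium level and decreasing the dose of magnesium sulfate, if needed". It goes on: "Study participation will continue; however, the timing and details of the dosing change will be recorded and used for research purposes". Treatment is open label: "it is not blinded and both the investigator and the research subject may know what dose of magnesium sulfate is being administered".

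Section 4 (Data Analysis) names one modelled outcome: "Univariate and multivariate mixed-effects modeling will be utilized to assess the impact of various covariates on the outcome of serum magnesium level". Section 6 provides for review by the principal investigator "Anytime that an AE, SAE, UP or protocol deviation is reported by an investigator or study staff", and for reporting to the IRB. Hypothesis 3 seeks the antenatal dose that keeps adverse drug effects low while the serum level stays therapeutic. Hypothesis 2 concerns correlation between serum level and side effects.

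**The concern.** The checks show who has a symptom at three moments. The response to a symptom can come at any moment and may itself remove the symptom. An episode that begins after one check, leads to a lower dose and is over by the next check leaves no trace in the Aim 2 comparison.

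The lowered dose does leave a trace, in the dosing record. Of everything the trial records, a reduction or discontinuation for symptoms comes closest to showing that a woman did not tolerate her assigned regimen. Hypothesis 3 is about that balance, yet no stated analysis sets this record side by side by arm. In an open-label trial, a general commitment to research use also leaves the choice of summary until after the data are seen.

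**Working it through.** **1. The provisions side by side.**

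| Item | When it is captured | Stated comparison of arms |
|---|---|---|
| Side effects (Aim 2; section 2) | 1 hour, 4 hours, delivery | Yes, as an aim; section 4 gives no method |
| Dose change for symptoms (section 2) | Any time | None; general research use only |
| Adverse events (section 6) | When reported | None; review and reporting only |
| Serum magnesium (Aim 1; section 4) | Baseline, 1 hour, 4 hours, delivery | Yes |

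**2. When an episode goes uncounted.** All of these must hold: it starts after one check, it has resolved by the next, and the woman has no symptom at any other check. A woman who also had symptoms at a check is counted there.

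**3. Length of the unobserved intervals.** Between the first two checks: 4 − 1 = 3 hours. Between the last two: T − 4, where T is hours from first dose to delivery. The documents give no T. If T is assumed to be 6, 12 or 24, the interval is 2, 8 or 20 hours. If delivery comes within 4 hours, there is no second interval.

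**4. The plan's own figure.** Aim 2 has none. The 18 per arm comes from Number of Subjects and concerns the 4-hour serum outcome. Alpha and power are not stated there. Assume two-sided 0.05 and 85% power, and take the stated 50-point difference as 45% vs 95%, so the mean proportion is 0.70:

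- m = [1.960 × √(2 × 0.70 × 0.30) + 1.036 × √(0.45 × 0.55 + 0.95 × 0.05)]² / 0.50² = 13.44
- with continuity correction: (m/4) × [1 + √(1 + 4/(m × 0.50))]² = 17.2, so 18 per arm.

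With 50% vs 95% and 80% power, the result is 15 without and 19 with the correction. The figure is reproducible under plausible assumptions. It is used below only as the number of women available.

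**5. What the added outcome could show with 18 per arm.** The rates are assumed, because the documents give none. They show precision only and are not evidence of bias.

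- Newcombe interval, with Wilson limits (l, u) for each arm: lower = d − √[(p1 − l1)² + (u2 − p2)²]; upper = d + √[(u1 − p1)² + (p2 − l2)²].
- Take 8/18 vs 4/18: d = 0.444 − 0.222 = 0.222. Wilson limits are 0.246 to 0.663 and 0.090 to 0.452.
- Lower = 0.222 − √(0.199² + 0.230²) = −0.082. Upper = 0.222 + √(0.218² + 0.132²) = 0.478.
- So the difference is 22.2 points, 95% CI −8.2 to 47.8.
- Exact power, two-sided Fisher test at 0.05: 0.247 for 25% vs 5%; 0.426 for 40% vs 10%; 0.193 for 8/18 vs 4/18.

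**The case against.** The strongest reply is that the plan is consistent. Aim 2 asks about three times, and side effects are collected at those times. It never promises to capture every episode, and a cumulative outcome is a different question. That stands: the aim and its data collection agree, and the three-check comparison should stay.

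The uncounted case is also narrow. The Background cites side effects in more than 77% of mothers given antenatal magnesium, so many women with an episode between checks may also have symptoms at a check. That stands too, and it is one reason why no size can be given.

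Third, the event is not lost, because the dose change is logged and adverse events are reviewed. That is true, but neither provision says that arms will be compared. Hypothesis 2 does not fill the gap, since it relates symptoms to serum level and not to assigned arm.

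Fourth, the added outcome has its own weakness. Staff who know the arm decide on reductions at their discretion, so the difference may partly reflect behaviour. This stands and limits the outcome to description.

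A reader might go further and infer that the delivery check understates harm at the higher dose. The documents do not support this. The direction depends on how many episodes occur and resolve in each arm, and no figure for either is given. Nor does any passage say that similar rates at the checks will be read as showing no excess of side effects. Wide intervals at this sample size come from the number of women, not from the timing of assessment.

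**Conclusion.** The point holds as an incompleteness in how Aim 2 serves Hypothesis 3. Women symptomatic only between checks are counted as symptom-free at every check, and the records that could reveal them enter no stated comparison of arms. This rests on reading the research use of dose changes in section 2 as unspecified, which is all the text allows.

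The size and direction of any distortion of the side-effect comparison are unknown. A reader might also fear for the 4-hour serum outcome. How symptoms between checks are counted does not enter it. The change is worth making because it uses data already recorded and bears on a stated hypothesis, but it is a secondary matter.

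**What to change.** Keep the comparison at the three checks. Add to Specific Aim 2 and section 4:

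1. A secondary descriptive outcome: the proportion of women with any dose reduction or discontinuation for symptoms from first dose to delivery. Compare by randomised arm, count each randomised woman once, and report a risk difference with 95% CI.
2. A reason-for-change field added to the dose-change details already recorded, so that reductions for symptoms can be told apart from others.
3. A table of reported adverse events by randomised arm over the same window.

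Delivery is the natural end of the window, because the dosing hypotheses are antenatal and the visit schedule stops there. Later reporting is optional, although the infusion continues for 24 hours after delivery.

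The cost is protocol and analysis wording plus one data field, with no new visits or samples and no change to dosing or care. The drawbacks should be stated with the outcome: low power at 18 per arm, open-label discretionary dose decisions, and a window whose length varies with time to delivery. The result should be presented as an estimate with its interval, not as a test of tolerability.
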